8.2.5. Final Evaluation Visit (Week 36) or Early Discontinuation

The following procedures must be performed and recorded at the Final Evaluation Visit for each subject. Following treatment, subjects will be followed for at a minimum of 24 weeks from LCL treatment and up to 36 weeks for safety or until maximal expression scores on the IGA-LCWS and PLCWS return to baseline or Week 36, whichever occurs first. Subjects will then have a Final Evaluation Visit at which time the following procedures must be performed and recorded:

- [REDACTED]
- 2. Conduct patient education: Discuss the potential effect of DAXI for injection treatment, explain the PLCWS measurement and the categories of the severity assessment scales, and instruct the subjects to consider depth of lines for severity of their LCL. Use the provided Patient Education Brochure
- [REDACTED]
- 10. Perform a physical examination [REDACTED]
- [REDACTED]
- 12. Measure and record vital signs (body temperature, respiratory rate, sitting radial pulse, and sitting systolic and diastolic blood pressure)
- [REDACTED]
- 14. Collect blood and urine samples for clinical safety laboratory tests (hematology, serum chemistry, and urinalysis)
- [REDACTED]

If there are no safety concerns, the subject's participation in the study is complete at this visit.

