This is a phase 2a, multicenter, open-label, dose-escalation study to evaluate the safety and efficacy of DAXI for injection for the treatment of subjects with moderate to severe LCL. This study will be conducted at 4 sites in the United States.

Approximately 64 subjects (18 to 65 years old) with moderate to severe LCL will be enrolled sequentially into 1 of 4 treatment cohorts (approximately 16 subjects per cohort) [REDACTED]

[REDACTED] Investigators will make all reasonable efforts to enroll equal proportions of subjects with moderate and severe LCL (based on baseline assessments) in each dosing cohort.

The total study duration will be up to 38 weeks, including up to 2 weeks for screening. Subjects will be followed for a minimum of 24 weeks from LCL treatment and up to 36 weeks or until scores on the maximal expression IGA-LCWS and PLCWS return to baseline, whichever occurs first. Subjects will then have a Final Evaluation Visit. Baseline, unless otherwise stated, refers to the last available assessment prior to LCL treatment (Day 1 Visit).

All treatments will be IM injections administered by the principal investigator (PI). [REDACTED]

[REDACTED]

[REDACTED]

[REDACTED]
 
[REDACTED]
 
[REDACTED]
 
[REDACTED]
 
[REDACTED] Revance has this right to stop or terminate the study at any time for any reason at their discretion or in consultation with the DRC.

Study Visits:
 
Study visits will occur at the Screening Visit (Day -14), Treatment Visit (Day 1), a safety follow-up phone call at Week 1, and follow-up visits at Weeks 2, 4, 8, 12, 16, 20, 24, 28, 32, and 36. Baseline for all efficacy assessments, unless otherwise noted, will be the last available assessment prior to LCL treatment (Day 1 Visit).

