
Efficacy Evaluations:
 
• IGA-LCWS• PLCWS• GAIS• FASE• FACE-Q™ Appraisal of Lines: Crow's Feet Lines 
Baseline for all efficacy assessments associated with LCL severity, unless otherwise noted, refers to the last available assessment prior to LCL treatment (Day 1 Visit). Efficacy outcomes derived from the above list of assessments will be summarized descriptively by dose group and by timepoint. Count and proportion will be provided for responder endpoints (defined as proportion of subjects achieving certain status). Kaplan-Meier (KM) curves will be plotted by treatment group for each time-to-event endpoint to assess median duration of effect at maximum smile and at rest for selected endpoints. Dose-response will be explored using logistic regressions on the response rates (of key responder endpoints) and using log-rank test on the time-to-event endpoints. The effect of study center and baseline severity on the treatment outcome will also be explored.

Safety Evaluations:

- Clinical laboratory tests (hematology, serum chemistry, prothrombin time [PT], urinalysis)
 - [REDACTED]
 - [REDACTED]
- Injection site evaluation
 - [REDACTED]
- Concomitant therapies/medications
- Collection of adverse events (AEs)
 - [REDACTED]
- Vital signs
- Physical examination: [REDACTED]

All TEAEs occurring during the study will be recorded and classified according to Medical Dictionary for Drug Regulatory Affairs (MedDRA) terminology. All reported TEAEs will be summarized, in terms of the number of subjects reporting events, system organ class, preferred term, severity, relationship to study drug, and severity. For summarization of event causality and severity, subjects will be counted only once within a system organ class or preferred term for a given event using the event with the greatest relationship for causality and the highest severity. A summary of AEs leading to discontinuation will also be provided.

A by-subject listing of any SAEs will be provided and all SAEs will be summarized by severity and relationship to study treatment.

All AEs, including TEAEs, and SAEs will be summarized for the study overall and by dose group.

Clinical laboratory tests, including serum chemistry, hematology, PT (at the Screening Visit only), and urinalysis will be collected at the Screening Visit, Week 4, and Week 36 or Final Evaluation Visit, if applicable. [REDACTED]

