4.4. Visit Schedule

A Screening Visit will be conducted up to 2 weeks prior to enrollment, and subjects will receive investigational product at baseline (Day 1). Following treatment, subjects will complete a paper diary for 2 weeks to capture their assessment of improvement in the appearance of LCL. A follow-up safety phone call will be conducted at Week 1. Post-treatment on-site follow-up visits

will occur at Weeks 2, 4, 8, 12, 16, 20, 24, 28, 32, and 36. The total study duration will be up to 38 weeks, including up to a 2-week screening period. Subjects will be followed for a minimum of 24 weeks post-treatment and up to 36 weeks or until scores return to baseline for the maximal expression IGA-LCWS and PLCWS or until the Week 36 Visit, whichever occurs first. Subjects will then have a Final Evaluation Visit.

Subjects will be evaluated for LCL severity using the Revance-validated 4-point IGA-LCWS and PLCWS at rest and at maximum smile effort.

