8.3.1. Investigator Global Assessment of Lateral Canthal Wrinkle Severity

At each clinic visit as designated in the SOA (Section 1.3), the investigator will assess the visual appearance (at rest and at maximum smile) of the LCL on each side of the face using the IGA-LCWS with the following 4-point scale (Table 4).

Table 4: Investigator Global Assessment Lateral Canthal Wrinkle Severity

Rating Score	Lateral Canthal Wrinkle Severity	Description
0	None	None to minimally visible line(s) lateral to the lateral canthus
1	Mild	Visible, shallow line(s) lateral to the lateral canthus
2	Moderate	Clearly visible, moderately deep line(s) lateral to the lateral canthus
3	Severe	Clearly visible, deep line(s) lateral to the lateral canthus with redundancy of skin

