8.3.2. Patient Lateral Canthal Wrinkle Severity Scale

Subjects will complete the PLCWS scale at rest and at maximum smile, to assess the severity of the LCL on each side of the face at the Screening Visit, Day 1 Visit (Baseline), follow-up visits, and the Week 36 Visit or the Final Evaluation Visit, if applicable.

The subject assessment form will be provided directly to the subject to complete while reviewing his or her LCL using the supplied handheld mirror. Scores at screening and baseline must be consistent bilaterally.

Refer to Appendix 4 for additional information.

Table 5: Patient Lateral Canthal Wrinkle Severity

Rating Score	Lateral Canthal Wrinkle Severity	Description
0	None	No line(s) lateral to the lateral canthus
1	Mild	Barely visible, shallow line(s) lateral to the lateral canthus
2	Moderate	Clearly visible, moderately deep line(s) lateral to the lateral canthus
3	Severe	Clearly visible deep line(s) lateral to the lateral canthus with redundancy of skin

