9.4.1. Efficacy Analyses

Unless otherwise noted, baseline for all efficacy assessments refers to the last available assessment prior to LCL treatment. Efficacy outcomes will be summarized. Descriptive statistics will be provided for all efficacy variables at all timepoints.

The primary efficacy endpoint will be the proportion of subjects achieving a score of 0 or 1 (none or mild) in LCL severity assessed by IGA-LCWS at maximum smile. The LCLs will be evaluated on both sides of the face and both scores will be recorded. If different ratings are obtained from the left and the right sides of the face, subjects will be scored using the higher (i.e., more severe) rating. The dose response in the proportion of responders at Week 4 will be explored using the logistic regression stratified by baseline LCWS severity and study center. Additional measures to assess the effectiveness outcomes will include the investigator GAIS evaluated at maximum smile at each visit. Various responder endpoints associated with the LCWS, such as achieving certain status or certain magnitude of improvement from baseline, will be derived from these effectiveness outcomes for each visit. These responder endpoints will be analyzed by statistical models similar to that for the primary endpoint.

Duration of response will be evaluated by various time-to-event endpoints. Kaplan-Meier (KM) curves will be plotted by dose group for each time-to-event endpoint.

Responder and time-event endpoints defined based on subject assessments for LCL wrinkle severity (such as PLCWS and the subject GAIS for LCL) will be summarized in the same way as those by investigator assessments. Similarly, the endpoints defined based on scores assessed at rest will be summarized in the same way as those on scores assessed at maximum smile.

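### Exit from Week 24 depends on maximum-smile scores alone, so Kaplan-Meier estimates of at-rest and GAIS duration after Week 24 are subject to dependent censoring; estimates through Week 24 are not

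*Protocol*

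**What the plan says.** **Follow-up.** The protocol synopsis (Overall Design) states "Subjects will be followed for a minimum of 24 weeks from LCL treatment and up to 36 weeks". Section 4.4 allows exit inside that window, "until scores return to baseline for the maximal expression IGA-LCWS and PLCWS", and Section 8.2.5 says the same: "until maximal expression scores on the IGA-LCWS and PLCWS return to baseline or Week 36, whichever occurs first". Section 4.1 agrees. None of these statements mentions scores at rest. On-site visits "will occur at Weeks 2, 4, 8, 12, 16, 20, 24, 28, 32, and 36", so early exit can remove up to three visits (Weeks 28, 32 and 36).

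**Planned duration analyses.** The synopsis (Efficacy Evaluations) plans Kaplan-Meier curves for time-to-event endpoints "to assess median duration of effect at maximum smile and at rest for selected endpoints", with log-rank tests to explore dose-response. Protocol 9.4.1 adds that "the endpoints defined based on scores assessed at rest will be summarized in the same way as those on scores assessed at maximum smile", and it names the subject GAIS among the sources of time-to-event endpoints. Protocol 9.4 plans no imputation.

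**Data collection.** At-rest severity is rated only at study visits. In 8.3.1, "the investigator will assess the visual appearance (at rest and at maximum smile) of the LCL on each side of the face"; in 8.3.2, "Subjects will complete the PLCWS scale at rest and at maximum smile". Nothing is recorded after exit.

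**SAP.** SAP 3.1 gives the exit rule without the qualifier that limits it to maximal expression. The only legible duration endpoint in SAP 6.5.3.2 is the composite return to baseline at maximum smile. The text around it is redacted.

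**The concern.** A subject whose two maximum-smile scores are back at baseline leaves at Week 24 or later, even if the lines at rest are still improved. The at-rest time is then censored at exit. Kaplan-Meier assumes that those censored have the same future risk as those who stay. Here those who leave have just lost the smile effect. If smile and rest effects wear off together, they are also nearer to losing the at-rest effect, and removing them makes the remaining curve look too good.

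The same applies to GAIS duration. The 7-point GAIS rates improvement and may still read improved when the 4-point severity scores have returned to baseline.

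At stake are the at-rest and GAIS curves after Week 24, any median that falls there, and the comparison of those curves between doses, because the share removed depends on each dose's smile duration. The maximum-smile composite is not at risk, because its event is what triggers exit. The Week 4 primary endpoint and the Week 4 committee reviews are not at risk either.

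**Working it through.** The documents give no expected duration at rest and no figure to reproduce. What follows is an illustration under assumptions.

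**Inputs from the documents.** The visit grid; minimum follow-up of 24 weeks; maximum of 36; exit at the later of Week 24 and the smile-return visit; about 16 subjects per cohort.

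**Assumed inputs.** Log-normal times with log-SD 0.35; median smile return (both scales) 22 weeks; median at-rest loss 28 weeks; correlation ρ between the two log-times; 400,000 simulated subjects per scenario.

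**Step 1: true at-rest survival.** S(t) = 1 − Φ(ln(t/28)/0.35).
- Week 24: 1 − Φ(−0.440) = 0.67
- Week 32: 1 − Φ(0.381) = 0.35
- Week 36: 1 − Φ(0.718) = 0.24

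**Step 2: share censored at Week 24 while still improved at rest.** Smile has returned by Week 24 in Φ(ln(24/22)/0.35) = Φ(0.249) = 0.60. At ρ = 0 the share is 0.60 × 0.67 = 0.40. At ρ = 0.8 the simulation gives 0.29.

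**Step 3: Kaplan-Meier under the exit rule.**

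| ρ | Week 36 at-rest KM | True |
|---|---|---|
| 0 | 24% | 24% |
| 0.3 | 31% | 24% |
| 0.5 | 35% | 24% |
| 0.8 | 46% | 24% |

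At Week 32 the reading is 45% at ρ = 0.5 and 52–53% at ρ = 0.8, against a true 35%. At ρ = 0.8 the curve implies that 0.46/0.67 = 69% of those improved at Week 24 remain so at Week 36. The truth is 0.24/0.67 = 36%.

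**Step 4: where the bias is absent or reversed.** Through Week 24 the curve is identical with and without the rule in every scenario. With smile median 22, rest median 30 and ρ = −0.3, Week 36 reads 0.217 against 0.302, which is too low. With smile median 26, rest median 18 and ρ = 0.9, almost nobody is censored early and there is no bias.

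**Step 5: the median (large sample, read on the visit grid, smile median 22).**
- Rest median 22: Week 24 with or without the rule, at every ρ examined.
- Rest median 26: Week 28 is unchanged up to ρ = 0.6; it becomes Week 32 at ρ = 0.9.
- Rest median 30: Week 32 is unchanged at ρ = 0.3; it becomes Week 36 at ρ = 0.6 and is not reached at ρ = 0.9.

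**Step 6: cohorts of 16 (smile 22, rest 30, ρ = 0.6).** The rule gives a later at-rest median than full follow-up in 65% of cohorts. The median is not reached in 50%, against 2% with full follow-up. Part of this is lost information rather than bias: at ρ = 0 it is not reached in 26%, against 2%. With rest median 22 and ρ = 0.6 the cohort median is unchanged in 97%.

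**Step 7: dose comparison.** Hold the at-rest distribution fixed (median 28, ρ = 0.5) and vary only the smile median. Week 36 at-rest KM reads 41% with smile median 18 and 28% with smile median 30; the truth is 24% in both. The dose with the shorter smile effect appears to last longer at rest.

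**The case against.** A reader might infer that at-rest duration will simply come out too long. The documents do not support that. Upward bias needs positive dependence between smile and rest durations, and an at-rest effect that outlasts the smile effect in some subjects. The median moves only if it lies beyond Week 24. The only legible duration figure, 4 to 5 months in the protocol introduction, describes botulinum toxin type A in general and falls before Week 24. This objection stands, and the point is conditional for that reason. Positive dependence is still the natural expectation for one injection session in one region, and the protocol schedules visits to Week 36, so it allows for effects beyond Week 24.

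A reader might also infer that the plan has no rule for this censoring. That cannot be said: the at-rest endpoint definitions, censoring rules and sensitivity analyses may sit in the redacted SAP text. It can only be said that the legible text contains none.

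Three further limits stand. First, eligibility sets a severity minimum at maximum smile only. Subjects with little or no line at rest have no at-rest effect to lose, so the at-risk set may be smaller than 16 per cohort, whereas the simulation gives everyone an at-rest event time. Second, the GAIS part rests on reasoning alone; it was not simulated. Third, the study is descriptive and not sized on power, so no confirmatory conclusion depends on these curves.

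**Conclusion.** The point holds in conditional form. Under the protocol's exit rule, at-rest and subject-GAIS Kaplan-Meier estimates after Week 24 are subject to dependent censoring. So are medians beyond Week 24 and dose comparisons of those curves. The at-rest bias is nil at zero correlation and upward at positive correlation when the at-rest effect outlasts the smile effect in some subjects. In the illustration it runs from 0 to 22 percentage points at Week 36 (24% to 46%, against a true 24%) for correlations from 0 to 0.8. These figures show direction and range under assumed distributions; they do not predict this trial's results.

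The exit rule itself also needs reconciling. The SAP wording could be read to cover scores at rest. If the study were run that way, the at-rest severity problem would largely go, but the GAIS problem would remain.

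**What to change.** **SAP wording, no new data:**
1. Run the main at-rest and GAIS duration summaries, and any log-rank comparison of them, only to Week 24. Report the event-free proportion at Week 24 and the restricted mean to Week 24. Define the cut by the nominal Week 24 visit, since the visit window is ±4 days.
2. Label any later at-rest or GAIS curve as subject to dependent censoring. Show beside it a lower bound that counts each smile-triggered exit as an event at exit. The bound will be wide: in the illustration at correlation 0.8 it already falls to 0.67 − 0.29 = 0.38 at Week 24.
3. Reconcile the exit rule in SAP 3.1 with Protocol 4.1, 4.4 and 8.2.5.

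**Cost.** A few sentences in the SAP. The downside is that there is no main at-rest or GAIS median beyond Week 24.

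**Optional.** The sponsor could instead require at-rest return before exit. That needs a protocol amendment and up to three more visits for subjects still improved at rest, and it does not resolve the GAIS endpoints.

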8.2.6. Variation from Scheduled Visit Days

To allow for scheduling flexibility, limited variation will be permitted from the specified time of each visit (Table 3).

Table 3: Allowed Variation from Scheduled Visit Days

Scheduled Visit	Allowed Variation
Week 1	+ 2 days
Week 2	± 2 days
Weeks 4, 8, 12, 16, 20, 24, 28, 32, and 36	±4 days

8.3. Efficacy Assessments

Effectiveness assessments will include investigator assessment of LCL severity and improvement, as well as subject assessment of severity and improvement. Effectiveness assessments will be conducted with the subject in a sitting position. To ensure consistent eye positioning during the assessment, the investigator should ask the subject to focus on a fixed point in the examination room. The assessment should be conducted in a room with good overhead lighting or natural light from a window (but not direct sunlight). Investigator assessments of improvement should be performed by the same evaluator throughout the study for a given subject. (Refer to Section 8.2.)

8.3.1. Investigator Global Assessment of Lateral Canthal Wrinkle Severity

At each clinic visit as designated in the SOA (Section 1.3), the investigator will assess the visual appearance (at rest and at maximum smile) of the LCL on each side of the face using the IGA-LCWS with the following 4-point scale (Table 4).

Table 4: Investigator Global Assessment Lateral Canthal Wrinkle Severity

Rating Score	Lateral Canthal Wrinkle Severity	Description
0	None	None to minimally visible line(s) lateral to the lateral canthus
1	Mild	Visible, shallow line(s) lateral to the lateral canthus
2	Moderate	Clearly visible, moderately deep line(s) lateral to the lateral canthus
3	Severe	Clearly visible, deep line(s) lateral to the lateral canthus with redundancy of skin

8.3.2. Patient Lateral Canthal Wrinkle Severity Scale

Subjects will complete the PLCWS scale at rest and at maximum smile, to assess the severity of the LCL on each side of the face at the Screening Visit, Day 1 Visit (Baseline), follow-up visits, and the Week 36 Visit or the Final Evaluation Visit, if applicable.

The subject assessment form will be provided directly to the subject to complete while reviewing his or her LCL using the supplied handheld mirror. Scores at screening and baseline must be consistent bilaterally.

Refer to Appendix 4 for additional information.

Table 5: Patient Lateral Canthal Wrinkle Severity

Rating Score	Lateral Canthal Wrinkle Severity	Description
0	None	No line(s) lateral to the lateral canthus
1	Mild	Barely visible, shallow line(s) lateral to the lateral canthus
2	Moderate	Clearly visible, moderately deep line(s) lateral to the lateral canthus
3	Severe	Clearly visible deep line(s) lateral to the lateral canthus with redundancy of skin

8.3.3. Global Aesthetic Improvement Scale (GAIS)

The investigator and subject will assess the visual appearance (at maximum smile) of the LCL improvement from the baseline condition on each side of the face using the following 7-point severity GAIS (Table 6). Subjects will use the baseline assessment photograph for comparison when reviewing the visual appearance for LCL to assess improvement following treatment. Assessments will be made as designated in the SOA (Section 1.3).

The Patient GAIS Assessment Form (Appendix 4) will be provided directly to the subject to complete while reviewing the lateral canthal treatment areas (at maximum smile) using the supplied handheld mirror as outlined in Appendix 5. Subjects with contact lenses should view

their treatment areas while wearing their contact lenses. Subjects who wear glasses must have sufficient visual acuity to be able to view their treatment areas without the use of glasses. The subject assessment must be completed before the investigator completes the IGA-LCWS assessment.

Table 6: Global Aesthetic Improvement Scale

Rating Score	Wrinkle Improvement
-3	Very Much Worse
-2	Much Worse
-1	Worse
0	No Change
1	Improved
2	Much Improved
3	Very Much Improved

8.3.4. Facial Age Self Evaluation (FASE)

At each clinic visit designated in the SOA (Section 1.3), the subject will be asked to rate their perceived age on a FASE questionnaire (Appendix 7). Following the subject’s completion of the Patient GAIS, the subject will be given the FASE questionnaire to rate their perception of how old they think they look following treatment.

8.3.5. FACE-Q™ Appraisal of Lines: Crow’s Feet Lines

At each follow-up visit designated in the SOA (Section 1.3), the subject will be asked to rate their perception of themselves on the FACE-Q Appraisal of Lines: Crow’s Feet Lines (Appendix 9). This questionnaire asks subjects to rate how bothered they are by their LCL using 7 questions about general appearance using a rating scale of 1 to 4 with 1 representing Not Bothered and 4 representing Extremely Bothered. Refer to Appendix 9 for additional information.

[REDACTED]

